5 PROJECT

6 PATIENTS AND METHODS

7 All patients with non-traumatic SCI consecutively admitted to three Italian SCI centers (IRCCS  
8 Fondazione Santa Lucia, Montecatone Rehabilitation Hospital and Istituti Clinici Scientifici  
9 Maugeri IRCCS of Pavia) between January 1st 2017 and June 30th 2020 have been prospectively  
10 enrolled in the study.

11 The study has been registered at [Clinicatrials.gov](https://www.clinicaltrials.gov).

12 The study was approved by the ethic committee of IRCCS Fondazione Santa Lucia and all the  
13 patients signed an informed consent to the study.

14 Inclusion criteria were: having a non-traumatic SCI in the acute / subacute phase with any level and  
15 severity (ASIA Impairment Scale) of injury and having a cognitive status that allows collaboration  
16 in the exam.

17 Exclusion criteria were the presence of dementia or cognitive decline; having a pathology of the  
18 peripheral nervous system that may affect the evaluation of ISNCSCI; having a multiple sclerosis.

19 The following data were prospectively recorded:

20 - Recording of demographic and clinical history data. Concerning the onset of lesion, for the  
21 ischemic and inflammatory groups reference was made to the appearance of the first symptoms,

22 while for the neoplastic and spondylogenetic myelopathies we referred to the date of surgical  
23 intervention which is usually accompanied by a worsening of the clinical picture.

24 - Evaluation of neurological conditions according to the International Standards For Neurological  
25 Classification of Spinal Cord Injury (ISNCSCI) (Revision 2015) (23) with registration of right and  
26 left motor and sensory level and of the Neurological Level of Injury (NLI), of the total motor score  
27 (MS), of upper extremities (UEMS) and lower extremities (LEMS) motor scores, light touch and  
28 pin prick sensory scores, and ASIA Impairment Scale (AIS). This assessment was carried out by  
29 two different experienced examiners (Table 1) in each center, 48-72 hours apart. One of the two  
30 examiners also assessed the functional status of the patients through the Spinal Cord Independence  
31 Measure (SCIM) version 2 or 3 (24).

32 - The patients were evaluated at admission with the possibility of repeating the evaluation also  
33 during rehabilitation stay and at discharge,.

34 Statistics

35 Descriptive statistics: mean and standard deviation (SD) for quantitative data; frequencies and  
36 percentages for qualitative ones. Normality of data was assessed by Shapiro-Wilk test. The NLI and  
37 the AIS grade have been transformed into numbers and treated as ordinal variables. For the NLI the  
38 level C1 corresponds to 1, and the level S4-5 to the number 29. For the AIS grade A correspond to 1  
39 and grade E to 5.

40 Validity and reliability represents the main measurement psychometric properties of instruments.  
41 The validity of instrument means that it measures what it is intended to measure. (25) while  
42 reliability refers to its stability over time (26).

43 Different aspects of reliability were assessed with appropriate tests: correlation (Spearman), test-  
44 retest reliability (Krippendorff's Alpha) and internal consistency (Cronbach's Alpha) (27, 28). For  
45 motor and sensory scores, we also compared the data of the two examiners by means of Wilcoxon  
46 matched pair test to evaluate if there was any significant difference.

47 As to the levels of injury (Neurological Level of Injury, left and right sensory and motor level of  
48 injury) and AIS grade the agreement between the two examiners regarding was assessed through the  
49 Krippendorff's Alpha. Furthermore, for the assessment of the levels, we compared the levels  
50 established by the two examiners, by counting the difference (1 level, 2 or more levels) in cases  
51 where assessments differed.

52 We evaluate psychometric properties of AIS scale on all sample and in each pathology subgroups.

53 As currently there is no gold standard for the neurological evaluation of persons with SCI other than  
54 the ISNCSCI, we have evaluated the convergent construct validity of the Standards through a  
55 Spearman correlation between the total motor scores, the upper and lower extremities motor scores  
56 and the total SCIM score as well as the subscores "Self-care" and "Mobility". This correlation was  
57 performed by means of Spearman test.

58 According to Landis and Koch (29), we interpreted ICC values and the level of agreement by  
59 Kappa-values as follows:  
60 0–0.1-virtually none  
61 0.1–0.4-slight  
62 0.41–0.6-fair  
63 0.61–0.8-moderate  
64 0.81–1-substantial  
65 All analyses were performed with SPSS 22.  
66 Significance was set at  $p < 0.05$   
67 Data have been reported according to the Guidelines For Reporting Reliability And Agreement  
68 Studies (GRRAS) (supplemental material, Table 15).

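### Krippendorff's alpha is labelled test-retest reliability, but the paired ratings come from two different examiners 48-72 hours apart, so it measures inter-examiner agreement over that interval

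*Combined protocol and SAP*

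**What the plan says.** Under PATIENTS AND METHODS, the neurological evaluation was done by "two different experienced examiners (Table 1) in each center, 48-72 hours apart". Eligible patients were in the early phase of injury: "Inclusion criteria were: having a non-traumatic SCI in the acute / subacute phase with any level and" severity. Further assessments were optional: "The patients were evaluated at admission with the possibility of repeating the evaluation also" during the stay and at discharge. No interval, examiner pairing or reliability analysis is given for them.

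The Statistics section states that "reliability refers to its stability over time (26"). It then lists the methods for different aspects of reliability, and alpha is given the test-retest role (the term is split over two lines): "retest reliability (Krippendorff's Alpha) and internal consistency (Cronbach's Alpha) (27, 28").

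The same section also describes alpha differently. For injury levels and "AIS grade the agreement between the two examiners regarding was assessed through the" same coefficient. Discrepant levels are those "established by the two examiners, by counting the difference (1 level, 2 or more levels) in cases" of disagreement. The motor and sensory scores get a Wilcoxon comparison: "motor and sensory scores, we also compared the data of the two examiners by means of Wilcoxon".

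**The concern.** Test-retest reliability asks whether the same measurement, repeated under the same conditions in an unchanged patient, gives the same answer. Here the second rating differs from the first in two ways: another person made it, and it was made two to three days later. Disagreement within a pair can therefore come from the examiners, from true change in an acute or subacute patient, or from random error.

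The plan names reliability as one of the two main measurement properties. A reader who takes the label at face value would credit the ISNCSCI with stability over time in non-traumatic injury, which this design does not test separately from examiner disagreement.

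**Working it through.** The plan states no figure for this point (no target alpha, sample size or expected disagreement), so there is none to reproduce. The check has four steps.

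**1. Text against text.**

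| Item | What the plan gives |
|---|---|
| Pairing | Two different examiners, 48-72 hours apart |
| Definition of reliability | Stability over time |
| Alpha, in the list of methods | Test-retest |
| Alpha, for levels and AIS grade | Agreement between examiners |
| Alpha, for motor and sensory scores | Not stated directly. The word *also* before the Wilcoxon test implies that alpha was used too; if so, test-retest is its only label |
| Same-examiner repeat | None described |

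One coefficient carries two labels for different properties, and only the inter-examiner label matches the pairing.

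**2. What the pairs can identify.** Write the rating variance as patient (P) + patient-by-examiner (E) + patient-by-day (D) + residual (R). With examiner 1 on day 1 and examiner 2 on day 2:

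- Var(y1) = P + E + D + R
- Var(y2) = P + E + D + R
- Cov(y1, y2) = P

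That is 2 independent equations for 4 unknowns. A same-examiner repeat would add a covariance of P + E (rank 3). A same-day second examiner would add P + D (rank 4). The mean difference equals examiner shift plus day shift: 1 equation for 2 unknowns if examiner order was fixed. If order was alternated, the mean shifts separate, but the variance components still do not.

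**3. Direction.** If ratings are independent and the error sources add, and T is the total variance, an agreement coefficient on these pairs reflects P/T. Same-day inter-examiner agreement would be (P + D)/T and same-examiner stability (P + E)/T. Since P/T is no larger than either, the planned coefficient understates both and inflates neither.

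**4. How much true change could matter (assumptions throughout).** The inputs are the plan's codings (AIS A-E as 1-5, NLI 1-29), ordinal-metric alpha, an assumed 150 pairs, perfect examiner agreement, and true change in random directions in 5%, 10% or 20% of pairs (8, 15 or 30 pairs).

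AIS, one-grade change:

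| Assumed mix A/B/C/D/E (%) | 5% | 10% | 20% |
|---|---|---|---|
| 20/20/20/20/20 | 0.986 | 0.974 | 0.947 |
| 15/10/25/50/0 | 0.971 | 0.948 | 0.899 |
| 5/5/20/70/0 | 0.934 | 0.884 | 0.791 |

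These values let grade D move to E. If it may not, the lowest cell falls to about 0.73.

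NLI, 20% of pairs changed:

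| Levels evenly used | One-level change | Two-level change |
|---|---|---|
| All 29 | 0.998 | 0.993 |
| 13 adjacent | 0.993 | 0.974 |
| 7 adjacent | 0.977 | 0.922 |

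A re-run of the ranks and of both tables agreed, with alpha values within about 0.003.

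**The case against.** The strongest reply is that the plan largely explains itself. It discloses the two examiners and the interval, it describes alpha as agreement between examiners for the levels and AIS grade, and it commits to a reporting guideline for reliability and agreement studies. The test-retest term appears once. On this view the point is editorial. It is true that a careful reader can work out what alpha measures. But the correct description covers only levels and AIS grade, and nothing withdraws the test-retest label or the definition it rests on. In a reliability study, which source of variation a coefficient reflects is the main question.

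Four further points stand, in whole or in part:

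- That alpha was applied to motor and sensory scores is an inference; no sentence says so outright.
- Results and conclusions are not in the documents, so no mistaken conclusion has been shown. The risk depends on how the label is read.
- The AIS illustration depends on assumed change rates and grade mixes, and its lower end moves with the rule for grade D. It shows how true change would act on alpha and does not measure the effect of the wrong label.
- An acute or subacute phase does not by itself prove change over two to three days. It means only that stability cannot be taken for granted.

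None of these supplies a same-examiner repeat, so none rescues the label.

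**Conclusion.** The concern holds. As written, the plan attributes to alpha a property that its pairing cannot isolate, and it contradicts its own description of the same coefficient. That conclusion follows from the text and the rank argument and needs no assumed values.

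The calculation of alpha is not at fault. As a measure of inter-examiner agreement at 48-72 hours it is valid, and under independent, additive errors it is conservative for both of the properties it might be mistaken for. The size of any contribution from true change is unknown. Under the stated assumptions it is small unless change is frequent and AIS grades are concentrated. The point should be corrected because it alters what the study can claim, but it does not threaten the analysis itself.

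**What to change.** - In the Statistics section, replace the test-retest label with inter-examiner reliability at a 48-72 hour interval. Use it wherever alpha is reported, including for motor and sensory scores if alpha was computed there.
- Bring the definition of reliability into line with this, and draw no test-retest or stability-over-time conclusion from these pairs.
- State as a limitation that examiner and day effects cannot be separated, and report whether examiner order was fixed or alternated.

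The cost is wording and a narrower claim: no new patients, assessments or re-analysis.

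An optional addition, which does not answer a demonstrated error: because each centre has its own examiners, show paired examiner differences by centre with 95% confidence intervals beside the Wilcoxon test, and do not read a non-significant p-value as showing no examiner difference. The data are already collected, but precision is limited. The half-width in SD units is t(0.975, n-1)/√n: 2.010/√50 = 0.28 at an assumed 50 patients per centre, against 1.976/√150 = 0.16 pooled at an assumed 150. If examiner order was fixed, these differences remain confounded with day.

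### Do optional repeat evaluations make the reliability and validity statistics treat several pairs from one patient as independent?

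*Combined protocol and SAP*

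**What the plan says.** Under Patients and Methods, each ISNCSCI assessment is made by "two different experienced examiners (Table 1) in each center, 48-72 hours apart", so one evaluation yields one pair of ratings. On timing the plan says: "The patients were evaluated at admission with the possibility of repeating the evaluation also" "during rehabilitation stay and at discharge". Admission is therefore the one evaluation that every patient has. Repeats are optional, and no schedule or number is given.

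Under Statistics, the methods are Spearman correlation, Krippendorff's alpha, Cronbach's alpha, a Wilcoxon matched-pairs test between examiners and a count of level disagreements. The relevant sentences include "motor and sensory scores, we also compared the data of the two examiners by means of Wilcoxon" and, for convergent validity against SCIM, "Spearman correlation between the total motor scores, the upper and lower extremities motor scores". The analysis set appears only in "We evaluate psychometric properties of AIS scale on all sample and in each pathology subgroups". The significance threshold is 0.05. Agreement is graded by bands of coefficient values. The section plans no confidence intervals, states no sample size, and does not say which time point or how many evaluations per patient are used.

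**The concern.** Put side by side, the two sections look incompatible. One lets a patient contribute several examiner pairs; the other uses methods whose standard forms assume one pair per independent subject. Pairs from the same patient share a lesion and plausibly the examiners, so they may be correlated.

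Two things would be at stake if all pairs went into one analysis. First, Wilcoxon and Spearman p-values would be too small, so significance would be claimed too readily. Second, patients evaluated more often would carry more weight in every coefficient, and a pooled motor-score-to-SCIM correlation would mix admission and discharge status. Both effects would matter most in small pathology subgroups.

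**Working it through.** The plan gives no sample size, power or precision figure, so there is nothing of its own to reproduce. The check has two parts: whether the text implies pooling, and how large the effect would be if pooling were assumed.

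**Does the text imply pooling?** No sentence under Statistics says that repeat evaluations enter the reliability or validity statistics. The whole sample is contrasted there with pathology subgroups ("We evaluate psychometric properties of AIS scale on all sample and in each pathology subgroups"), which reads naturally as all patients against groups of patients. The methods listed fit the admission pair, or each time point analysed separately. Pooling is thus one possible reading and not the most natural one.

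**Size under assumed pooling.** The inputs are:

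- Nominal level 0.05, from the plan. It states no sidedness; two-sided is assumed, so z = 1.96.
- Evaluations per patient, m: assumed 2 or 3. The plan gives no number.
- Within-patient correlation r of the between-examiner differences: assumed 0 to 0.5. The plan gives none. This is not the stability of the patient's score; it is whether the gap between the two examiners persists from one occasion to the next.

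The design effect is DEFF = 1 + (m − 1) × r, and the true error is 2 × [1 − Φ(1.96/√DEFF)].

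| m | r | DEFF | 1.96/√DEFF | true error |
|---|---|---|---|---|
| 1 | any | 1.00 | 1.960 | 5.0% |
| 2 | 0.1 | 1.10 | 1.869 | 6.2% |
| 2 | 0.3 | 1.30 | 1.719 | 8.6% |
| 2 | 0.5 | 1.50 | 1.600 | 11.0% |
| 3 | 0.1 | 1.20 | 1.789 | 7.4% |
| 3 | 0.3 | 1.60 | 1.549 | 12.1% |
| 3 | 0.5 | 2.00 | 1.386 | 16.6% |

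Simulated Wilcoxon tests (60 patients assumed, 4,000 runs per setting) agree: 8.3% and 10.5% for m = 2, and 11.9% and 15.3% for m = 3, at r = 0.3 and 0.5. With one evaluation per patient the simulated error was 4.3% to 5.3%. At r = 0 it was 5.4% for m = 2 and 4.9% for m = 3. Null Spearman tests, with the same within-patient correlation in both variables, were affected less: 7.8% (m = 2) and 11.1% (m = 3) at r = 0.5.

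**Optional repeats.** The table gives every patient two or three evaluations, whereas the plan makes repeats optional. With unequal numbers, m is replaced by Σm²/Σm. If 30% of patients had one repeat, that is (0.7 × 1 + 0.3 × 4)/(0.7 × 1 + 0.3 × 2) = 1.9/1.3 = 1.46. For r = 0.1, 0.3 and 0.5, DEFF is 1.046, 1.138 and 1.231, and the true error is 5.5%, 6.6% and 7.7%.

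**Weighting.** If 50%, 30% and 20% of patients had one, two and three evaluations, the mean would be 0.5 + 0.6 + 0.6 = 1.7, and the 20% with three would supply 0.6/1.7 = 35% of the pairs. This too arises only under pooling, and it shifts a coefficient only if agreement differs between patients seen often and patients seen once.

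**What pooling could not affect.** No confidence intervals are planned, so no stated precision could be overstated. No p-value is described for either alpha, and agreement is graded on the size of the coefficient. For the Wilcoxon test, excess false positives would show examiner differences that do not exist, which counts against a claim of reliability.

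**The case for a change.** The strongest case for acting is that two analysts could follow this text and get different results from the same data: one takes the admission pairs, the other stacks every evaluation. The Statistics section is silent on the unit of analysis. It also describes reliability as stability over time and labels Krippendorff's alpha a test-retest measure, so a reader may wonder whether later evaluations belong in the coefficients. One sentence would remove the doubt, and under pooling the inflation is real and confirmed by simulation.

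It stands that the unit of analysis and the time point are not stated, and that the named methods in standard form do not allow for several pairs per patient. It does not stand that the plan commits to stacking. The test-retest label is already explained by the two examinations 48 to 72 hours apart within one evaluation; it does not need the discharge data. Nor does the plan link the number of repeats to length of stay, since a discharge evaluation is possible after any stay. Extra weight for long-stay patients is therefore an inference.

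**Conclusion.** The concern does not call for a change. What is missing is a detail that an analyst would sensibly fill: one pair per patient, at admission, the only evaluation every patient is sure to have, with any later evaluations reported separately. Handled that way, the error stays at 5% and no patient is over-weighted. No rule in the plan would itself produce a wrong result.

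The adverse figures hold only if evaluations were pooled and examiner differences were positively correlated within patients. They run from about 6% to 17% with two or three evaluations for everyone at correlations of 0.1 to 0.5, and from about 5.5% to 7.7% with 30% repeating once. The number of repeats, the correlation and the 60 patients used in the simulations are all assumptions. A reader of the results can settle the matter by checking that the number of pairs analysed equals the number of patients.

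### For the motor and sensory scores, no stated analysis shows the spread of disagreement between the two examiners in points

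*Combined protocol and SAP*

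**What the plan says.** Under Patients and Methods, each patient is assessed by "two different experienced examiners (Table 1) in each center, 48-72 hours apart". The point scores recorded are the total motor score (MS), its upper and lower extremity parts (UEMS, LEMS), light touch and pin prick.

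The Statistics section then states the following.

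- Descriptive analysis: "Descriptive statistics: mean and standard deviation (SD) for quantitative data; frequencies and" percentages for qualitative data. Paired differences are not named.
- Reliability: Spearman correlation, Krippendorff's alpha (called test-retest reliability) and Cronbach's alpha (internal consistency).
- An addition for the scores: "motor and sensory scores, we also compared the data of the two examiners by means of Wilcoxon", followed by "matched pair test to evaluate if there was any significant difference".
- For the levels of injury only, a comparison of those "established by the two examiners, by counting the difference (1 level, 2 or more levels) in cases" where the examiners did not agree.
- An interpretation scale, introduced with "we interpreted ICC values and the level of agreement by" Kappa values. Its top band is "0.81–1-substantial". The ICC appears here but not in the list of analyses.

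The word *also* in the Wilcoxon sentence suggests that the three coefficients apply to the motor and sensory scores too, although the text does not say so outright. The section closes by saying that reporting follows the GRRAS guideline, with a supplemental table that is not part of the available document.

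**The concern.** A reader of a two-examiner reliability study wants to know how far apart two assessments of the same patient can be, in the units of the score. That is what tells a later user whether an observed change in motor score exceeds measurement error.

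Neither kind of stated analysis answers this. A reliability coefficient compares disagreement with the variation between patients, so the same coefficient can go with small differences in a homogeneous sample or large ones in a varied sample. The Wilcoxon test asks whether one set of scores tends to be higher than the other. If disagreement is purely random, it is non-significant about 95% of the time, however large the disagreement is. A high coefficient beside a non-significant Wilcoxon could then be read as close agreement in points, which neither result establishes.

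The plan already counts the size of disagreement for levels, so the omission for the scores is a gap in its own approach.

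**Working it through.** The documents give no sample size, score SD or expected coefficient, so there is no figure of the plan to reproduce. The check has two parts: what each stated analysis can deliver, and how much room that leaves under assumed values.

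**1. Stated analyses for the scores, against the question of spread in points**

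| Stated analysis | Units | Shows a systematic shift? | Shows the spread of paired differences? |
|---|---|---|---|
| Spearman | none | no | no |
| Krippendorff's alpha (metric not stated) | none | only mixed with spread | only if converted using a score SD |
| Cronbach's alpha | none | no | no |
| Wilcoxon matched pair | p-value | yes | no |
| Mean and SD per examiner, if tabulated | points | by subtraction | no |
| Count of differences by size | levels | not applied to scores | not applied to scores |

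**2. From coefficient to points.** For an absolute-agreement coefficient c on an interval metric, score SD S and negligible mean difference:

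SD of differences = S × √(2 × (1 − c)); 95% limits = ±1.96 × SD of differences.

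All values of S and c are assumptions. The value 0.81 is the lower edge of the plan's top band. At c = 0.81, √(2 × 0.19) = 0.616; at c = 0.95, √(2 × 0.05) = 0.316.

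| Assumed S | c = 0.81: SD of differences | Limits | c = 0.95: SD of differences | Limits |
|---|---|---|---|---|
| 10 | 6.2 | ±12.1 | 3.2 | ±6.2 |
| 15 | 9.2 | ±18.1 | 4.7 | ±9.3 |
| 20 | 12.3 | ±24.2 | 6.3 | ±12.4 |
| 25 | 15.4 | ±30.2 | 7.9 | ±15.5 |

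The row for S = 10 is there because UEMS and LEMS are parts of the total motor score and may vary less. A simulation with the ICC held at 0.95 and total SDs of 10, 20 and 30 gave a Spearman correlation of 0.945 each time, while the SD of differences rose from 3.2 to 6.3 to 9.5 points.

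**3. Examiner means and SDs do not fill the gap.** Suppose both examiners have the same mean and an SD of 20. The SD of differences is 20 × √(2 × (1 − r)), where r is the paired correlation.

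- r = 0.98: 20 × √0.04 = 4.0, limits ±7.8.
- r = 0.85: 20 × √0.30 = 11.0, limits ±21.5.

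The two tables of means and SDs would be identical.

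**4. Wilcoxon with no systematic shift.** Simulated differences were normal with mean 0, rounded to whole points, tested two-sided at 0.05 (the plan does not state sidedness), with 60, 120 or 200 pairs and 3,000 runs per setting.

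| SD of differences | Non-significant | Pairs more than 5 points apart |
|---|---|---|
| 3 | 95-96% | 7% |
| 5 | 95-96% | 27% |
| 10 | 95-96% | 58% |

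A separate simulation with 50 and 100 pairs rejected in 4.7% to 6.5% of runs for SDs of 2, 5 and 10. This follows from how the test is built. It is shown only to make clear that the p-value carries no information about spread.

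**The case against.** The strongest reply is that nothing stated is invalid. Krippendorff's alpha is a chance-corrected agreement coefficient, a shift test beside it is a sensible pair, and the spread can be roughly recovered from an interval-metric alpha and the score SD. This stands in part: one useful summary is missing, and the rest need not be discarded. But the recovery needs a metric that the plan does not state and a step that it does not plan.

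A second reply is that GRRAS reporting would cover this. The supplemental table is not available, so what was reported is unknown. A reporting guideline is in any case not a stated analysis.

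A third is that limits of agreement would not isolate examiner error. This is correct. With assessments 48-72 hours apart in acute or subacute patients, paired differences mix examiner disagreement with any true change. Repeat evaluations during the stay are also allowed, so pairs from one patient may not be independent. Both points shape the fix.

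A fourth is that the illustration rests on assumptions. It does. In addition, the plan states its bands for ICC and Kappa values, so attaching 0.81 to Krippendorff's alpha is an extension, and one range of SDs need not suit all five scores.

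A reader might also infer that a pooled Wilcoxon would hide opposite biases in the three centers. That requires pooling, examiner labels that are arbitrary across centers, and a systematic gap within centers. The documents state none of these, and Table 1, cited for the examiners, is not visible. If examiner 1 means the first assessment, a pooled signed difference is well defined.

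**Conclusion.** The point holds as a gap in what the plan will report, and it should be closed. For MS, UEMS, LEMS, light touch and pin prick, the stated analyses leave the spread of disagreement in points unknown. This follows from the text and does not depend on any assumed value.

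Its practical size cannot be fixed from the documents. Under assumed score SDs of 15 to 25 points and an interval-metric absolute-agreement coefficient, results that all fall within 0.81 to 0.95 span limits from about ±9 to about ±30 points.

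The documents do not support the conclusion that agreement was poor, that the coefficients or the Wilcoxon test are wrong, or that one center's examiners differ systematically.

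**What to change.** For each of the five scores, using one pair per patient (for example at admission) or a method that allows for repeated pairs:

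- Report the mean paired difference, second minus first assessment, with a 95% CI.
- Report the SD of the paired differences with 95% limits of agreement, percentile-based if the differences are not normal.
- Add a summary that does not depend on labelling: the within-patient SD, √(Σd²/2n), or counts of pairs by size of difference in points, as the plan already does for levels.
- Keep the Wilcoxon as a check for shift, and do not read a non-significant result as agreement.
- State that the differences include any true change over 48-72 hours.

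Mean differences by center are an optional descriptive check.

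The cost is slightly more analysis of data already collected, with no new visits. Precision is the main limit in small samples. The 95% CI half-width for the mean is t × SD/√n. For each limit of agreement it is t × SD × √(1/n + 1.96²/(2(n − 1))). With an assumed SD of differences of 4 to 8 points, these give 1.3-2.6 and 2.2-4.4 points at 40 independent pairs, and 1.9-3.7 and 3.3-6.5 at 20. Percentile-based limits are less stable still at such sizes.

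### The Wilcoxon comparison of the two examiners ignores which of them went first, so unless order was balanced it can create or hide an examiner difference

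*Combined protocol and SAP*

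**What the plan says.** Under Patients and Methods, eligibility covers "having a non-traumatic SCI in the acute / subacute phase with any level and" severity. The neurological assessment is done by "two different experienced examiners (Table 1) in each center, 48-72 hours apart. One of the two" also scores functional status. There are three centres, so the examiner pair differs by site. On timing, "The patients were evaluated at admission with the possibility of repeating the evaluation also" during the stay and at discharge, so only the admission assessment is certain.

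The Statistics section states that for "motor and sensory scores, we also compared the data of the two examiners by means of Wilcoxon" "matched pair test to evaluate if there was any significant difference". It also says that "reliability refers to its stability over time (26"), a definition that does not distinguish elapsed time from the rater.

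The available text does not say who examined first, or whether order was fixed, alternated or randomised. It describes no check that the patient was stable between the two examinations and no analysis term for occasion. Examination dates and order are not named in the list of recorded data.

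**The concern.** Each pair of scores differs in two respects: who examined, and when. The Wilcoxon test is set up by examiner only. If one examiner tends to go first, then recovery, deterioration or familiarity with the examination between visits enters the comparison as if it were an examiner effect. If that change and a real examiner bias have opposite signs, they offset each other and the bias is missed.

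What is at stake is the reading of the result. A significant test may reflect the patients' course, and a null test may be two effects cancelling. Without knowing the order, a reader cannot tell whether either applies.

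**Working it through.** **Inputs from the documents.** Two examiners per centre, 48-72 hours apart, paired Wilcoxon, significance at 0.05 (sidedness not stated; two-sided assumed). The documents give no sample size, SD, expected change or order, so there is no plan figure to reproduce.

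**Assumed inputs.** SD of paired differences 4 points; 100 or 150 pairs; mean change 0.5 or 1 point; examiner bias 0 or 1 point in size; scores rounded to whole points.

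**Model.** Call the examiners A and B. Let b be the bias of A relative to B, c the mean change from first to second examination, and q the share of pairs in which B went first.

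- B first: mean of A − B = b + c
- A first: mean of A − B = b − c
- Pooled, as the plan analyses it: b + (2q − 1)c

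The pooled shift is b + c when B always goes first (q = 1), b + 0.6c at an 80:20 mix, and b at 50:50.

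**Creating a difference (b = 0).** A normal approximation to the rejection rate is Φ(z − 1.96), with z = shift × √n / SD. The Wilcoxon simulation should fall slightly below it.

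| Order | Change | Pairs | z | Approximation | Simulated Wilcoxon |
|---|---|---|---|---|---|
| Fixed | 1 | 100 | 1 × 10 / 4 = 2.50 | 71% | about 69% |
| Fixed | 1 | 150 | 1 × 12.25 / 4 = 3.06 | 86% | about 85% |
| Fixed | 0.5 | 100 | 0.5 × 10 / 4 = 1.25 | 24% | about 23% |
| Fixed | 0.5 | 150 | 0.5 × 12.25 / 4 = 1.53 | 33% | about 32% |
| 80:20 | 1 | 100 | 0.6 × 10 / 4.08 = 1.47 | 31% | about 30% |
| 80:20 | 1 | 150 | 0.6 × 12.25 / 4.08 = 1.80 | 44% | about 42% |
| 50:50 | 1 | either | 0 | 5% | about 5% |

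At 80:20 the SD is √(16 + 4 × 0.8 × 0.2 × 1²) = 4.08, because mixing the orders adds spread.

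**Range over SD.** With order fixed, only change / SD matters. If the SD is 8, a 1-point change behaves like 0.5 point at SD 4 (about 23% and 32%). If the SD is 2, a 0.5-point change behaves like 1 point at SD 4 (about 69% and 85%).

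**Hiding a difference (b = −1, c = +1, 150 pairs).** With B always first the shift is −1 + 1 = 0, so the bias is detected about 5% of the time, against about 85% when there is no change. At 80:20 the shift is −1 + 0.6 = −0.4, z = 0.4 × 12.25 / 4.08 = 1.20, and detection is about 20%.

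**What separates the two.** Averaging the orders with equal weight gives [(b + c) + (b − c)] / 2 = b. Second minus first is b + c when B went first and −b + c when A went first; the equal-weight average is c.

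The standard error of the examiner estimate is (SD / 2) × √(1/n₁ + 1/n₂). With 120 and 30 pairs this is 2 × √(0.00833 + 0.03333) = 0.41, against 4 / √150 = 0.33 for balanced order. For a 1-point bias, z = 1 / 0.41 = 2.45, so power is about 69% (simulated 68%, with about 5% false rejection whatever the change).

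**What does not separate them.** A − B within a single order is b + c or b − c, so it is still confounded. Suppose b = c = 1 with 75 pairs in each order: the two strata have means 2 and 0. Requiring the shift to be significant in both strata finds the bias in only about 2% of studies. The plan's own pooled test finds it in about 85% at this balanced order.

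**The case against.** The strongest reply is that the whole effect depends on order, and the documents are silent on it. If order was balanced within centres, mean change drops out and the plan's test keeps its 5% error rate. This stands. A reader might infer that examiner and time effects are inseparable by design; that needs one examiner always to have gone first, which the documents do not say.

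A reader might also infer that patients did change materially over two to three days. The documents do not show this. The remark that surgery is an "intervention which is usually accompanied by a worsening of the clinical picture" explains how onset was dated in two aetiology groups; it does not describe the interval between the two examinations. Distortion also needs a net change in one direction across mixed aetiologies, and that could be small.

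Three further objections stand in part.

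- Examiners differ by centre, so a single bias across all sites is a simplification. This is why the estimate should be made within centre.
- The Wilcoxon supplements Spearman, Krippendorff's alpha, Cronbach's alpha and the counts of level differences. The same interval also affects agreement measured by alpha and by the counts, so the issue is not confined to this test. The Wilcoxon is, however, the comparison aimed at a systematic difference between examiners.
- Data collection is described in the past tense, so order can no longer be balanced. It can still be analysed if it was recorded.

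**Conclusion.** The point holds conditionally. The plan compares examiners who saw patients at different times and takes no account of order, so without knowing the order the Wilcoxon result cannot be attributed to the examiners. In the illustrative setting (SD 4, 100-150 pairs, 0.5-1 point mean change, fixed order), false rejection runs from about 23% to 85%. An 80:20 order still gives about 30% to 42% for a 1-point change. A balanced order gives about 5%. All these rates rest on assumed values and show what could happen, not what did. The concern is about what conclusion the test can support; it does not show that the reported scores are wrong.

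**What to change.** 1. State how examination order was decided and, by centre, how many patients each examiner saw first.
2. Where dates or order are available, code first versus second examination. For each motor and sensory score, within each centre, estimate the examiner effect as the equal-weight average of the A − B differences in the two orders. Estimate the time effect as the equal-weight average of the second-minus-first differences in the two orders. Give both with confidence intervals.
3. Do not read A − B within a single order as the examiner effect, and do not require it to persist in each order separately.
4. Where one examiner always went first, or order cannot be recovered, label the shift as examiner plus elapsed time. Draw no conclusion about examiner bias from a significant or a null Wilcoxon result.
5. Optionally, repeat the analysis on discharge evaluations, but only where both examiners rated.

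**Cost.** A few lines of analysis and no new visits, provided dates or order were kept, which the documents do not confirm. The price is precision: in the example above the standard error rises from 0.33 to 0.41 at 80:20. Strata by centre are smaller still: with an assumed 50 pairs in a centre, it would be 4 / √50 = 0.57 if balanced and 2 × √(1/40 + 1/10) = 0.71 at 80:20.
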